Irritability/Agitation:	17-35
Anxiety:	12-42
Dizziness:	3-50
Confusion:	10-42
Headache:	13-42

Other less frequent symptoms include vivid dreams, insomnia, nausea, sweating, and electric shock feelings (“zaps”). In rare cases (<1%), suicidal thoughts have occurred (Fava et al, 2015).

An “antidepressant discontinuation syndrome” has been defined in the research literature as the occurrence of 4 or more new or worsened psychic or physical symptoms that arise after stopping an antidepressant (Rosenbaum et al, 1998). Rates of ADM discontinuation syndrome have ranged from 14 – 60% (Baldwin et al, 2006; Khan et al, 2014; Rosenbaum et al, 1998; Sir et al, 2005; Tint et al, 2008).

Most of the research on discontinuation symptoms conducted to date has focused on symptoms arising after cessation of drugs that block the serotonin transporter (selective serotonin reuptake inhibitors, SSRIs, or serotonin norepinephrine reuptake inhibitors, SNRIs). However, before the SSRIs were developed, discontinuation symptoms had been noted to occur with the older tricyclic antidepressants, and case reports have been published for other newer antidepressants that do not affect the serotonin transporter (Dilsaver, et al, 1987). The standard in clinical practice is now to taper off SSRIs and SNRIs, though there is no widely accepted taper rate or protocol to follow when tapering (Ogle et al, 2012). Tapering is often not performed with other classes of antidepressants, though data that could inform clinicians about discontinuation symptoms from those medications is sparse.

Previous controlled studies of antidepressant discontinuation have been conducted on patients who have benefitted from the medication and were willing to be tapered off. The prior randomized discontinuation studies limited to patients who have not responded to their antidepressant had small sample sizes (Tint et al, 2008). Some data suggests that antidepressant side effects at drug initiation may predict eventual treatment response if patients adhere to the medication. It is theorized that certain side effects may reflect the responsivity of biological systems (such as monoamine signaling systems) to the antidepressant (Renoir, 2013). Extending this model to discontinuation suggests that non-responders to medication may have fewer side effects when discontinuing the antidepressant.

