Clinical practice would be enhanced if predictors of difficulty tapering ADM could be identified. Currently, very little is known about which patients are likely to develop discontinuation symptoms. The most consistently replicated finding is that the long half-life antidepressant fluoxetine is associated with fewer discontinuation symptoms than the short half-life agent paroxetine. However, discontinuation symptoms are known to arise with fluoxetine cessation, and both these drugs are SSRIs. Identification of patients who will or will not develop difficulty coming off antidepressants is of significant clinical importance because tapers that are longer or shorter than necessary can negatively impact patient care.

This study will aim to assess the frequency of discontinuation symptoms across all classes of antidepressants among patients who have not responded to medication. Only patients who wish to be tapered off their medication will be eligible to participate.

Objectives:

There are two primary objectives to this study:

AIM 1: Compare the tolerability of two antidepressant tapering regimens.

Hypothesis 1. Tapering antidepressant dose over two weeks will be associated a lower incidence of antidepressant discontinuation symptoms than tapering over one week.

Hypothesis 2. Discontinuing medications that inhibit the serotonin transporter (SSRIs and SNRIs) will show greater difference in the frequency of discontinuation symptoms between the two week and one-week tapering regimens than medications that do not inhibit the serotonin transporter.

AIM 2: Identify demographic and clinical features that predict the emergence of antidepressant discontinuation symptoms.

Hypothesis 2. SSRIs and SNRIs will be associated with greater numbers of discontinuation symptoms compared to non-SSRI/SNRI medications.

Hypothesis 1. Duration of treatment will positively associated with the number of discontinuation symptoms.

Study Design and Methods:

Sample

The sample will include 125 subjects currently taking an FDA-approved antidepressant. We anticipate an approximate screen fail rate of 20%, allowing for 100 subjects to enter randomization.

Inclusion Criteria:

1. Male or female, age 18-75
2. Currently taking an FDA-approved antidepressant for at least four weeks.
3. Primary psychiatric diagnosis of major depressive disorder, an anxiety disorder, OCD, or PTSD.
4. Ability to read and understand English language

Exclusion Criteria for all Subjects:

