HAMA	X	X	X	X
DESS	X	X	X	X
PWC-20		X	X	X
Patient Ratings				
DEBS	X	X	X	X
BIS	X	X	X	X
Q-LES-Q	X			X
PGI-C		X	X	X
SAD (Daily)	X	X	X	X
Safety Measures				
Concomitant Meds	X	X	X	X
Adverse Events		X	X	X
CSSRS	X	X	X	X

Taper Regimens:

Taper A:

Days 1-7: Take 50% of baseline dose
Days 8-14: Take 25% of baseline dose
Day 15: Stop antidepressant

Taper B:

Days 1-3: Take 50% of baseline dose
Days 4-7: Take 25% of baseline dose
Day 8: Stop antidepressant

Monitoring for Suicidality

The emergence of suicidal thoughts or behaviors are not considered part of antidepressant discontinuation symptoms, but rather are thought to reflect the breakthrough of a new depressive episode. Patients who do not believe their antidepressant is helping them may nevertheless experience worsening depression with discontinuation of the medication. Therefore, we will conduct a standardized assessment for suicidal ideation or behavior, the CSSRS, at every study visit. Any patient who exhibits and increase in suicidal ideation, any form of suicidal behavior, or about whom the study physician has concern for their safety will be immediately withdrawn from the study and treated as clinically appropriate.

Operationalized Discontinuation Criteria for Suicidality:

Research participants are exited from the study should any of the following occur:

- Any emergent CSSRS defined suicidal behavior
- A suicidal ideation score of 5 (indicating active suicidal ideation with specific plan and some level of intent) on the CSSRS
- In the absence of a CSSRS suicidal ideation score of 5 or CSSRS-defined suicidal behavior, the investigator determines the patient to have a significant short-term risk for a suicide attempt.

Randomization:

Patients will be randomized in a 1:1 manner to Taper A or Taper B. Randomization will be stratified based on mechanism of action of drug (serotonin reuptake inhibitor or not). The two randomization schedules will be created prior to study commencement by a staff member not involved in the clinical components or data analytic components of the study. Randomization assignments will be placed in numbered and sealed envelopes, and opened sequentially for each subject who qualifies for randomization at Visit 1.

Included Medications:

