Secondary analyses will include a similar 2-way ANCOVA assessing change from baseline in PWC-20 and SAD peak daily scores between the two taper groups following the same analytic plan as for the DESS. The proportion of patients experiencing the ADM discontinuation syndrome in each taper arm will be compared by Chi-Square test. The frequency of individual discontinuation symptoms between the two taper arms will be assessed using Fisher's Exact Test.

Power Calculation:

An sample size of 48 patients per taper group provides 80% power to detect a clinically meaningful difference of 1.0 points on the DESS, with a standard deviation of 1.75 (at two-sided $\alpha=.05$). With 49 subjects per taper group, we will have 70% power to detect a difference of 20% (10% vs 30%) incidence in ADM discontinuation syndrome.

Adverse event reporting:

Risks to participation

Risks to participation include experiencing side effects from the taking or discontinuing antidepressant medications. All study antidepressants share some risks, including headache, nausea, anxiety, sleep and appetite disturbance. In patients under age 25, antidepressant initiation and dose increase has been associated with a small increased risk of developing thoughts of self-harm or suicidal ideas.

Benefits to subject or future benefits

Patients who participate will receive an expert psychiatric assessment and treatment. With treatment, patients may be able to come off ineffective or no longer desired antidepressant medication. Patients will have the benefit of participating in a clinical trial that could inform future treatment of patients with antidepressants.

Training:

No training will be necessary for the rating scales used in this study because all research personnel involved in this project as they are currently trained and involved in ongoing clinical trials with mentally ill patients.

Confidentiality:

Patient's confidentiality will be maintained throughout the duration of their study participation. Patient files will be kept in locked offices, and the computerized data is kept on password-protected computers in the locked Mood and Anxiety Disorders Program offices.

Informed consent:

At the screening visit, patients will be provided with an informed consent form that will outline the risks and benefits of participating in this study. It will also outline which assessments occur at the various study visits.

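### The secondary syndrome comparison ignores the drug-class stratum used in randomization; a stratified test is a cheap improvement, though the planned chi-square is valid and the gain is probably small

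*Combined protocol and SAP*

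**What the plan says.** **Randomization.** "Patients will be randomized in a 1:1 manner to Taper A or Taper B", and "Randomization will be stratified based on mechanism of action of drug (serotonin reuptake inhibitor or not"). On how this is done, the section says: "The two randomization schedules will be created prior to study commencement by a staff member not involved in the clinical components". It gives no block size and does not mention blocking.

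**Objectives, Aim 2.** "SSRIs and SNRIs will be associated with greater numbers of discontinuation symptoms compared to non-SSRI/SNRI medications". No size is given for this effect. Aim 1 adds the hypothesis that the taper difference itself is larger for drugs that inhibit the serotonin transporter.

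**Outcomes and Statistical Analysis.** The syndrome is a secondary outcome, reached at four or more new or worsened DESS symptoms. The test is given in one sentence: "The proportion of patients experiencing the ADM discontinuation syndrome in each taper arm will be compared by Chi-Square test". The sentence names no stratification, adjustment, effect estimate or continuity correction. Drug class is also missing from the candidate covariates listed for the DESS analysis, and the second factor of the 2-way ANCOVA is not named.

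**Power Calculation.** "With 49 subjects per taper group, we will have 70% power to detect a difference of 20% (10% vs 30%) incidence in ADM discontinuation syndrome".

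**The concern.** When randomization is stratified on a factor that predicts the outcome, the analysis should normally use that factor. Here the protocol itself expects drug class to predict discontinuation symptoms, and the syndrome is a threshold on the same DESS count. A pooled chi-square compares the arms against a null variance that includes the spread between classes. If the arms are balanced within class, that spread cannot contribute to the observed difference, so the test is somewhat too cautious. If they are not balanced, chance class imbalance adds noise that a stratified test would remove. Either way some power may be lost, and at 70% this comparison has little to spare. It is one of only two outcomes for which the plan states a power.

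**Working it through.** **Inputs from the documents.** 49 per arm; overall syndrome rates 10% v 30%; 1:1 allocation; two strata. The two-sided 5% level is stated for the DESS calculation ("with a standard deviation of 1.75 (at two-sided") and is assumed to carry over to the syndrome.

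**Inputs that had to be assumed.** The background gives a published range of syndrome rates ("Rates of ADM discontinuation syndrome have ranged from 14" up to 60%) but does not split it by class. The reuptake-inhibitor share was therefore set at about 50%, 70% or 80%, and the class risk ratio (reuptake inhibitor to other) at 1, 2, 3 or 5, equal in both arms. Overall rates were held at 10% v 30%.

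**Step 1: reproduce the stated power.** Power = Φ[(Δ√n − 1.96√V0)/√V1], with V0 = 2p̄(1−p̄) and V1 = p1(1−p1) + p2(1−p2).

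- Δ√n = 0.20 × √49 = 1.40
- V0 = 2 × 0.20 × 0.80 = 0.32
- V1 = 0.09 + 0.21 = 0.30
- (1.40 − 1.96 × 0.5657)/0.5477 = 0.532, so power = 70.3%

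The plan's 70% is right for the planned test. Exact enumeration gives 72.5% without continuity correction and 62.7% with it.

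**Step 2: one stratified case in full.** Take class risk ratio 3 and an even split. The 10% arm is then 15%/5% by class, the 30% arm 45%/15%, and the class means 30%/10%.

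- Within-class null variance: ½(2 × 0.3 × 0.7) + ½(2 × 0.1 × 0.9) = 0.30, against 0.32 pooled
- Variance under the alternative, arms balanced within class: ½(0.1275 + 0.2475) + ½(0.0475 + 0.1275) = 0.275
- Chi-square: (1.40 − 1.96√0.32)/√0.275 = 0.555, power 71.1%
- CMH: (1.40 − 1.96√0.30)/√0.275 = 0.623, power 73.3%
- True size of the chi-square under no taper effect (overall rate 20%): 2[1 − Φ(1.96√(0.32/0.30))] = 4.3%

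**Step 3: the range.** Gain is CMH power minus chi-square power, in points, across the three class splits. Simulations used 400,000 trials per scenario and no continuity correction.

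| Class risk ratio | CMH power, approximation | Gain, approximation | Gain, simulated, arms balanced within class | Gain, simulated, unblocked |
|---|---|---|---|---|
| 1 | 70.3% | 0 | about −0.9 | about −0.9 |
| 2 | 70.9–71.6% | 0.5 to 1.0 | −0.4 to +0.1 | −0.2 to +0.3 |
| 3 | 71.4–73.4% | 0.9 to 2.3 | +0.2 to +1.5 | +0.4 to +2.0 |
| 5 | 72.1–76.0% | 1.3 to 4.2 | +0.8 to +3.3 | +1.1 to +4.4 |

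The larger figures in each row come from the even split. If the taper effect is confined to reuptake inhibitors (others 10% in both arms), simulated power with balanced strata is 73.8% v 75.0% at the even split, 73.0% v 72.9% at 70% and 72.9% v 72.7% at 80% (chi-square v CMH).

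**Step 4: extreme class differences, even split.**

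- Class rates 18%/2% v 55%/5% (risk ratios 18/2 = 9 and 55/5 = 11): 74.5% v 79.9% with balanced strata, 71.9% v 79.1% unblocked. Gains are 5.4 and 7.2 points.
- No syndrome at all outside the reuptake-inhibitor class: 75.8% v 83.4% balanced, 72.2% v 83.2% unblocked. Gains are 7.6 and 11.0 points.

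**Step 5: type I error at a common overall rate of 20%.** With arms balanced within class, the simulated size of the nominal 5% chi-square is 5.2% at ratio 1, 4.8–5.1% at ratio 2, 4.5–4.9% at ratio 3 and 3.9–4.8% at ratio 5. With unblocked schedules it is 5.0–5.1% throughout. CMH stays at 4.9–5.1%.

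**The case against.** A reader might infer that the chi-square must be conservative because randomization is stratified. The documents do not support that. Two separate schedules balance the arms within class only if they are blocked or otherwise restricted, and the Randomization section does not say so. Without blocking, the test holds its level. A size as low as about 1.5% needs class rates such as 60%/5% together with enforced balance; the overall null rate is then (60 + 5)/2 = 32.5%, above both rates used in the power calculation. At 30%/10% with an even split the size is about 4.5% even with balance.

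A reader might also infer a power loss of 5 points or more. That needs risk ratios of about 9 or higher and an even split. Aim 2 gives a direction only, and the published range is not split by class.

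Nor is stratifying strictly free: CMH gives up about 1 point if class is not prognostic. The unstated continuity correction matters more, at 72.5 − 62.7 = 9.8 points of exact power.

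All of this stands. It does not remove the reason to stratify. The power argument does not depend on blocking, since CMH also removes chance class imbalance under unblocked schedules. The likely loss is about 1 point if the protocol's own hypothesis is wrong, against a larger gain if class differences are large.

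**Conclusion.** The point holds as a recommendation for efficiency and for consistency between design and analysis. The syndrome analysis leaves out a factor that the trial randomizes on and expects to be prognostic. The planned test is nevertheless valid: its type I error is not materially inflated with or without blocking, and its stated 70% power is correct. It is conservative only if class is prognostic and the arms are balanced within class.

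At overall rates of 10% v 30%, the effect of stratifying is about −1 point of power at ratio 1, about 0 to 2 points at ratios 2 to 3, up to about 4 at ratio 5, and about 5 to 11 only at ratios of about 9 or more with an even split. These figures rest on assumed class risk ratios and splits, because the documents give neither. Under moderate assumptions the change does not materially repair the 70% power. The outcome is secondary, so the primary comparison is untouched.

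**What to change.** In Statistical Analysis, replace the chi-square sentence with a prespecified Cochran-Mantel-Haenszel test of the syndrome by taper arm, stratified by drug class as randomized and without continuity correction. Report the stratum-adjusted risk difference with its 95% CI, and keep the unstratified chi-square as a sensitivity check, stating that it too is uncorrected. In Randomization, state whether the two schedules are blocked.

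The cost is a sentence or two of text. The stratum is already recorded for every randomized patient, so no new data or patients are needed. The statistical price is about 1 point of power if class turns out not to be prognostic.

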1. Clinician ratings of symptoms: MADRS, HAMA
2. Clinician rating of suicidality: CSSRS
3. Clinician assessment of discontinuation symptoms: DESS, PWC-20
4. Vital signs (temperature, height, weight, blood pressure, pulse)
5. Review of concomitant medications and supplements
6. Review of adverse events

7. Patient questionnaires: DEBS, BIS, PGI-C

Visit 3:

Visit 3 occurs 2 weeks after initiating the antidepressant taper. The following procedures will be performed:

1. Clinician ratings of symptoms: MADRS, HAMA
2. Clinician rating of suicidality: CSSRS
3. Clinician assessment of discontinuation symptoms: DESS, PWC-20
4. Vital signs (temperature, height, weight, blood pressure, pulse)
5. Review of concomitant medications and supplements
6. Review of adverse events
7. Patient questionnaires: DEBS, BIS, PGI-C

Visit 4:

Visit 4 occurs 3 weeks after initiating the antidepressant taper. The following procedures will be performed:

1. Clinician ratings of symptoms: MADRS, HAMA
2. Clinician rating of suicidality: CSSRS
3. Clinician assessment of discontinuation symptoms: DESS, PWC-20
4. Vital signs (temperature, height, weight, blood pressure, pulse)
5. Review of concomitant medications and supplements
6. Review of adverse events
7. Patient questionnaires: DEBS, BIS, PGI-C, Q-LES-Q
8. Planning of transition of care.
9. Download of SAD daily scale data from website sad.ecu.edu.

Multiple potential referral options will be discussed, depending on the patient's improvement and insurance status. Final referral selected will be based on the patient's preference. Options include referral to a primary care physician, psychiatrist, therapist, community mental health center, or other research studies. If necessary, patients may be seen for 1 or 2 post-study follow-up visits until their care transfer is completed.

Schedule of Events:

BIS: Barratt Impulsiveness Scale; CSSRS: Columbia Suicide Severity Rating Scale; DEBS: Dunlop Emotional Blunting Scale; DESS: Discontinuation Emergent Signs and Symptoms; HAM-A: Hamilton Anxiety Rating Scale; MADRS: Montgomery Asberg Depression Rating Scale; MINI: Mini-International Neuropsychiatric Interview; PGI-C: Patient Global Impression, Change; PWC-20: Physician Withdrawal Checklist; Q-LES-Q: Quality of Life Satisfaction Questionnaire

Visit Number	V1	V2	V3	V4
Day	0	7	14	21
Informed consent	X			
Demographics	X			
Vital signs	X	X	X	X
Weight	X			X
Psych/Medical History	X			
MINI v.7.0	X			
Clinician Ratings				
MADRS	X	X	X	X

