Plans to inform participants of new findings or research results that might affect health:

If new findings emerge regarding risks or benefits of the study medications used in our study, patients will be informed of this information as soon as possible and reminded of their ability to continue participation in the study at their own will.

Data and safety monitoring plan (DSMP):

The tapering regimens provided in this protocol are consistent with standard-of-care for MDD, OCD, PTSD and anxiety disorders. It is expected that some patients will experience the known antidepressant discontinuation symptoms – these will not be classified as adverse events. Any unanticipated mental or physical symptoms that are not anticipated as adverse events (i.e., not listed on the DESS scale), or any breaches of confidentiality or other social harms will be coded as adverse events. We will review the adverse event data twice-yearly to evaluate whether unexpected frequencies of adverse events are occurring.

Plans for data management and monitoring:

Data will be stored on an Excel spreadsheet on a password-protected computer, stored in our research clinic.

Pharmaceutical, biologic, and device information:

Package inserts for the antidepressants that could be used in the study are available at <http://dailymed.nlm.nih.gov/dailymed/about.cfm>

APPENDICES

Questionnaires and scales attached include:

Hamilton Anxiety Rating Scale (HAM-A)

Montgomery Asberg Depression Rating Scale (MADRS)

Dunlop Emotional Blunting Scale (DEBS)

Barratt Impulsiveness Scale (BIS)

Quality of Life, Enjoyment, and Satisfaction Questionnaire (Q-LES-Q)

Mini Neuropsychiatry Interview, Version 7.0 (MINI)

Discontinuation Emergent Signs and Symptoms (DESS)

Physician Withdrawal Checklist (PWC-20)

Columbia Suicide Severity Rating Scale (CSSRS)

Scale for Anxiety and Depression (paper version)

REFERENCES

Baldwin DS, et al. A double-blind, randomized, parallel-group, flexible-dose study to evaluate the tolerability, efficacy and effects of treatment discontinuation with escitalopram and paroxetine in patients with major depressive disorder. *International Clinical Psychopharmacology*, 2006; 21:159-169.

Dilsaver SC, et al. Antidepressant withdrawal syndromes: phenomenology and pathophysiology. *International Clinical Psychopharmacology*, 1987; 2:1-19.

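### Known discontinuation symptoms are exempt from adverse event coding with no exception for serious cases, so a serious reaction would miss the twice-yearly safety review

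*Combined protocol and SAP*

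**What the plan says.** The DSMP expects some patients to have the known discontinuation symptoms and states that "these will not be classified as adverse events". What it does code is "Any unanticipated mental or physical symptoms that are not anticipated as adverse events (i.e., not listed on the DESS scale"), together with confidentiality breaches and other social harms. The review is then defined on that set: "We will review the adverse event data twice-yearly to evaluate whether unexpected frequencies of adverse events are occurring".

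Elsewhere the protocol treats discontinuation effects as a risk to participants. Under Adverse event reporting it says: "Risks to participation include experiencing side effects from the taking or discontinuing antidepressant medications". That section goes on to risks and benefits only. It gives no definition of a serious event and no reporting route.

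The symptoms are measured closely. Visits 2, 3 and 4 each include "Clinician assessment of discontinuation symptoms: DESS, PWC-20", and the DESS is also taken at Visit 1. In the Schedule of Events, the block headed "Safety Measures" holds concomitant medications, adverse events and the CSSRS. The DESS and PWC-20 are placed among the clinician ratings.

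Suicidality is handled separately under Monitoring for Suicidality, with the CSSRS at every visit and its own exit criteria.

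**The concern.** The exemption is defined by type of symptom, not by severity or consequence. A mild symptom that nobody anticipated is coded and reviewed. A known symptom that puts a patient in hospital is, on the wording, not coded and so not reviewed. The background section counts worsened mood, agitation and confusion among the most frequent discontinuation symptoms, so the exempt class includes symptoms that can be severe.

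At stake is whether the people reviewing safety twice a year would learn of a serious reaction to either taper through the route the protocol gives them, and whether such a reaction would be recorded as a serious event at all.

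**Working it through.** The plan gives no figure on this point, so the check is to follow the rules as written.

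**Step 1. Is there an exception anywhere?**

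| Section | What it adds for a serious known symptom |
|---|---|
| DSMP | Exempts known symptoms; no mention of seriousness, hospital care or withdrawal |
| Adverse event reporting | Risks and benefits only |
| Monitoring for Suicidality | Allows withdrawal of a patient over whom the physician has a safety concern; says nothing on recording or reporting |
| Operationalized exit criteria | Suicidality only |
| Schedule of Events | Adverse events reviewed at Visits 2 to 4, under the DSMP definition |

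No section supplies one.

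**Step 2. Follow four cases through the plan.**

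| Case | Coded as adverse event? | In twice-yearly review? | In outcome analysis? |
|---|---|---|---|
| Mild, unanticipated, not on the DESS | Yes | Yes | No |
| Known symptom, not serious, patient returns | No | No | Yes |
| Known symptom, serious, patient returns | No | No | Yes, as a DESS symptom and a PWC-20 rating |
| Known symptom, serious, patient never returns | No | No | No |

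In the third row, the outcome data do not carry what makes the event serious. Under Measures, the DESS assesses the frequency of symptoms and the PWC-20 their intensity. Neither is described as recording a hospital admission or other medical care.

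The fourth row follows from Statistical Analysis. The modified ITT sample requires at least one post-randomization visit, and the PWC-20 and SAD analyses follow the same plan. Daily SAD entries might exist for such a patient, but the download is scheduled for Visit 4 and no earlier review is described.

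**Step 3. What can be sized?** The Power Calculation assumes that 10% and 30% of patients have the discontinuation syndrome (four or more new or worsened DESS symptoms). With 100 randomized 1:1, that is 50 × 0.10 + 50 × 0.30 = 5 + 15 = 20 patients. At the 14% to 60% cited in the background it is 100 × 0.14 = 14 to 100 × 0.60 = 60 patients.

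These counts cover any severity. They show how much duplicate coding would follow if every DESS symptom were made an adverse event, which is a reason to keep the exemption for ordinary cases. They do not measure the gap. The documents give no rate of serious discontinuation reactions, so the number of affected patients cannot be derived from them.

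**The case against.** The strongest reply is that the exemption is deliberate and sound. New or worsened DESS symptoms are the primary outcome, and coding them again as adverse events would count them twice. Patients are seen weekly for three weeks by clinicians who rate these symptoms. This stands for ordinary symptoms, and the fix keeps it. It does not explain the absence of an exception for serious ones.

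A second reply is that the DSMP does not mention hospital admission, so the gap is read from silence, and that the DESS items are in an appendix not reproduced in the text reviewed. Both are fair. But the exemption reaches all known discontinuation symptoms, and the background names the common ones, so the reading does not depend on the item list. Nor do the documents say that any other reporting rule overrides the exemption.

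A reader might also infer more than the documents support:

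- *That the main harm of the tapers escapes safety monitoring.* It does not. Clinicians rate the DESS and PWC-20 at every post-baseline visit, and a physician's safety concern leads to withdrawal (a clause in the suicidality section). What is missing is adverse event coding and the periodic review.
- *That suicidal thoughts are exempted too.* The background does say "In rare cases (<1%), suicidal thoughts have occurred", but Monitoring for Suicidality states: "The emergence of suicidal thoughts or behaviors are not considered part of antidepressant discontinuation symptoms". They are tracked by the CSSRS with separate exit criteria.
- *That the published results would understate harm.* An adverse event table alone would omit these symptoms, but the plan compares DESS change, the syndrome and each individual symptom between arms.
- *That the symptom rates in the background give the size of the problem.* Those percentages count symptoms of any severity, and the protocol itself calls such rates inconsistent across studies.

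**Conclusion.** The point holds in a limited form. As written, a serious discontinuation reaction would not be coded as an adverse event and would not appear in the twice-yearly review. If the patient never returned after randomization, it would appear in no planned safety or outcome summary at all.

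The number affected is unknown and probably small. The case for change rests on the consequence of a single such event and on how little the change costs. The conclusion assumes that the DSMP is applied literally and that no reporting rule outside these documents overrides it. It does not bear on the regimens, the sample size or the primary analysis.

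**What to change.** Amend the DSMP along these lines: *A symptom listed on the DESS is recorded as an adverse event if it meets the seriousness criteria stated in this protocol, leads to study withdrawal, or leads to unscheduled medical care. Other DESS-listed symptoms are recorded on the DESS only.* The protocol must then state the seriousness criteria, since it now gives none. Events recorded this way enter the existing twice-yearly review without further change.

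Optionally, add early-withdrawal and discontinuation-syndrome counts to that review, pooled across arms only. The study team carries out the review and the plan has no interim rule, so counts by arm would be unplanned looks at data closely tied to the primary outcome.

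The cost is slightly more adverse event coding. Adverse events are already reviewed at Visits 2 to 4, so no visit or scale is added. One limit remains: for a patient who does not return, the new rule lets the event be recorded only if the team learns of it.
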